7.0 STATISTICAL CONSIDERATIONS

7.1 Statistical Analyses

Twenty-nine evaluable patients will have 80% power to declare a significant decrease in ICU admissions from a historical control of 50% of hospitalized patients to 25% with a two-sided type I error of 0.05 (reject ICU admission rate=50% if only 8 or less patients are admitted to ICU among 29 evaluable patients). The historic control group will consist of 29 patients who are gender and age (within 5 years) matched.

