1.0 SUMMARY

Background: There are currently no proven treatment options for Coronavirus Disease 2019 (COVID-19) caused by Severe Acute Respiratory Syndrome Coronavirus 2 (SARS-CoV-2). Human convalescent immune plasma infusion (CIP) is an option for treatment of COVID-19.

Clinical Experience: Passive antibody therapy for infections has been used since the late 1800s and prior to the development of antimicrobial therapy in the 1940s^{1,2}. There is some evidence that convalescent plasma can provide neutralizing antibodies to SARS-CoV-2³. Convalescent serum was used in the 2013 Ebola epidemic. A small non-randomized study in Sierra Leone revealed a significant increase in survival for patients treated with convalescent whole blood compared to those who received standard treatment⁴.

Primary Objective: Evaluate whether CIP can reduce progression of critical illness among patients hospitalized for COVID-19

Primary Endpoints:

1. Transfer to the intensive care unit (ICU)
2. 28 day mortality

Secondary Objectives:

1. Evaluate the safety of CIP.
2. Evaluate cellular and humoral responses before CIP treatment and at CIP treatment.
3. Evaluate the effect of CIP as compared to non-transfused immunologic control patients.

Secondary Endpoints:

- Cumulative incidence of serious adverse events during the study period: transfusion reaction (fever, rash), transfusion related acute lung injury (TRALI), transfusion associated circulatory overload (TACO), transfusion related infection
- Rates and duration of SARS-CoV-2 PCR positivity at days 0, 4, 7, 14 and 21.
- Serum or plasma antibody titer¹ to SARS-CoV-2: Day 0, 7, 14, and 28
- Cellular and humoral immune responses at days 0, 7, 14, and 28 days
- Supplemental oxygen free days
- Ventilator free days
- ICU free days
- Sequential organ failure assessment (SOFA) score at days 0, 1, 2, 17, 14, 21, 28
- Need for vasopressors
- Need for renal replacement therapy
- Need for extracorporeal membrane oxygenation (ECMO)
- Hospital length of stay (LOS)
- ICU LOS
- Grade 3 or 4 adverse events (AEs)

Study Design: This is a single arm phase II trial to assess efficacy and confirm safety of infusions of anti-SARS-CoV-2 convalescent plasma in hospitalized patients with acute respiratory symptoms, with or without confirmed interstitial COVID-19 pneumonia by chest Xray or CT. A total of 29 eligible subjects will be enrolled to receive anti-SARS-CoV-2 plasma. Outcomes will be compared to hospitalized controls

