2.3 Study Design

This is a single arm phase II trial to assess preliminary efficacy and confirm safety of infusions of anti-SARS-CoV-2 convalescent plasma in hospitalized patients with acute respiratory symptoms **with or without** confirmed interstitial COVID-19 pneumonia by CXR or chest CT. A total of 29 eligible subjects will be enrolled to receive high titer anti-SARS-CoV-2 plasma. Participants will be compared to a historical control group via retrospective chart review.

In addition, the following Immunologic Controls will be used to meet secondary objectives described above:

1. PBMCs with 5-10 million cryopreserved cells per specimen will be obtained from the prospective COVID 19 Biorepository (2 timepoints per patient t (60 specimens total) and assessed for cellular and humoral immune responses.
2. Serum or plasma 500 UI each from up to 50 patients in the Covid-19 Biorepository will be collected (2 timepoints from each patient) (100 total specimens) will be evaluated for antibody and cytokine responses.

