3.2 Experience with the use of convalescent immune plasma against coronavirus diseases

In the 21st century, there were two coronavirus epidemics associated with high mortality. The SARS outbreak in 2003 and MERS outbreak in 2012 had high mortalities and absence of effective therapies which led to the use of convalescent immune plasma. The largest study with SARS using convalescent immune plasma involved the treatment of 80 patients in Hong Kong⁷. **Patients treated before day 14 after onset of symptoms had an improved prognosis as measured by discharge from hospital before day 22.** Furthermore, those who were RT-PCR positive and seronegative for coronavirus at the time of therapy had improved prognosis. Three seriously ill patients recovered from SARS in Taiwan were treated with 500 ml of convalescent plasma which led to a reduction in plasma virus titer⁸. Three patients with MERS in South Korea were treated with convalescent plasma, but only two of the recipients had neutralizing antibody in their plasma⁹. The results suggests that providing passive antibodies may suppress the development of high titers of neutralizing antibodies to the pathogen¹⁰. The analysis of 99 samples of convalescent sera from patients with MERS showed that 87 had neutralizing antibody with a geometric mean titer of 1:61. These data suggest that antibody declines with time and/or that few patients make high titer responses. There are reports that convalescent plasma was used for therapy of patients with COVID-19 in China during the current outbreak. Although few details are available from the Chinese experience and published studies involved small numbers of patients, the available information suggests that convalescent plasma administration reduces viral load and was safe. Because of these early suggestions of benefit, it is ethically complex to conduct a placebo-controlled trial, therefore we propose to use a comparator group of patients who have been treated at UVA Medical Center prior to the start of this trial.

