5.2.6 Subject Removal

Subjects should be removed from the trial if they require >6L/min supplemental oxygen or mechanical ventilation prior to receiving convalescent plasma infusion. Subjects may receive other medications that the investigator deems to be medically necessary.

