9.0 STATISTICAL CONSIDERATIONS

9.1 Power calculation

Twenty-nine evaluable patients will have 80% power to declare a significant decrease in ICU admissions from a historical control of 50% of hospitalized patients to 25% with a two-sided type I error of 0.05 (reject ICU admission rate=50% if only 8 or less patients are admitted to ICU among 29 evaluable patients).

Data analysis: For categorical clinical endpoints, frequency with percentage will be summarized. For the quantitative clinical variables and immune response variables measured in this objective, we will produce summary statistics (including means, medians, and standard deviations) for data at pre- and post-CIP infusions. Subsequent analyses will compare the serologic and neutralization antibody titers for anti-SARS-COV-2 antibodies and immune response variables (after a suitable data transformation to improve normal distribution, if necessary) pre- and post-treatment using a paired t-test (or Wilcoxon sign ranked test if the data are not approximately normally distributed). The level of each measured immune biomarker measured at the follow-up time points will be plotted to visually show the change of immune responses over time. To explore whether immune responses at pre- or peak improvement at post-CIP infusions associate with clinical endpoints (such as ICU admission, intubation), logistic regression for binary endpoints and Cox regression for time to event endpoints will be used to analyze each measured immune biomarker respectively. These effects will be compared to biospecimen from non-transfused immunologic controls. Analyses will adjust for other covariates such as age and co-morbidities. No

multiplicity adjustment is planned due to the nature of being exploratory. A two-sided p-value of < 0.05 will be considered significant.

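### The 8-of-29 ICU rule has 71% exact power, not 80%; its error rate rests on an unsourced 50%, and the 80% does not carry over to the comparison with matched controls, whose entry point differs from the recipients'.

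*Combined protocol and SAP*

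**What the plan says.** Sections 7.1 and 9.1 carry the same power statement: "Twenty-nine evaluable patients will have 80% power to declare a significant decrease in ICU admissions from a historical control of 50% of hospitalized patients". The alternative rate is 25% and the two-sided type I error 0.05. Both give the same decision rule: "reject ICU admission rate=50% if only 8 or less patients are admitted to ICU among 29 evaluable patients". Neither cites a study, a chart count or a range for the 50%, and no other section does.

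The plan also promises a comparison with patients who did not receive plasma. The Summary says "Outcomes will be compared to hospitalized controls"; section 2.3 says "Participants will be compared to a historical control group via retrospective chart review". Section 3.2 offers this group in place of a placebo arm: "we propose to use a comparator group of patients who have been treated at UVA Medical Center prior to the start of this trial". Section 7.1 fixes its size and matching: "The historic control group will consist of 29 patients who are gender and age (within 5 years) matched".

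For analysis, section 9.1 says "For categorical clinical endpoints, frequency with percentage will be summarized". The only control comparison it describes is with the immunologic biospecimen controls. It gives no test, interval or power for ICU transfer against the 29 matched patients.

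On entry, section 4.1 takes recipients with respiratory symptoms within 72 hours of admission who are not in ICU, and section 5.2.6 adds: "Subjects should be removed from the trial if they require >6L/min supplemental oxygen or mechanical ventilation prior to receiving convalescent plasma infusion". Section 4.3 applies the ventilation and 6 L/min limits to controls only at the time of admission, and does not require respiratory symptoms of them.

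**The concern.** ICU transfer is the only endpoint with a power statement and a decision rule, so the properties of that rule are the trial's efficacy properties. Three things looked wrong.

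- The stated power did not seem to fit so strict a cut-off.
- A fixed-null rule is only as sound as its null. If untreated floor patients on 6 L/min or less go to ICU less often than half the time, the rule can succeed with no treatment effect.
- Because the rule and the 29 controls stand side by side in section 7.1, the 80% could be read as covering both. A pass on the rule could then be taken as evidence against the controls, who are selected at a different point in the hospital stay.

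**Working it through.** **Inputs.** From 7.1 and 9.1: n = 29, null rate 0.50, alternative 0.25, two-sided 0.05, reject if X ≤ 8, stated power 80%. From 7.1: 29 matched controls. From 4.1, 4.3 and 5.2.6: the entry conditions. The untreated rates other than 50%, and the early-deterioration fraction d below, are assumptions, because the documents give neither.

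**1. Reproducing the 80%.** One-sample normal approximation without continuity correction:

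- N = [(1.96 × √(0.5 × 0.5) + 0.842 × √(0.25 × 0.75)) / 0.25]² = 28.92, rounded up to 29.
- Power at 29 = Φ[(0.25 − 1.96 × 0.0928) / 0.0804] = Φ(0.846) = 80.1%.

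So 29 and 80% are correct for that method.

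**2. The printed rule, exactly.** With X binomial(29, p):

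| Cut-off | P(reject) at 0.25 | Lower tail at 0.50 | Twice lower tail |
|---|---|---|---|
| ≤ 8 | 71.3% | 1.2% | 2.4% |
| ≤ 9 | 83.4% | 3.1% | 6.1% |

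The uncorrected z-test would also reject at 9 of 29, where z = (9/29 − 0.5)/0.0928 = −2.04. The printed cut-off of 8 is instead the exact one with each tail held to 0.025. The plan has paired the power of one test with the cut-off of another. With 0.025 per tail, no cut-off at 29 reaches 80%.

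**3. Dependence on the 50%.** P(X ≤ 8 of 29) with no treatment effect, by assumed untreated rate:

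| Untreated rate | 60% | 55% | 50% | 45% | 40% | 35% |
|---|---|---|---|---|---|---|
| Rule succeeds | 0.04% | 0.3% | 1.2% | 4.3% | 11.9% | 26.5% |

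The nominal 2.5% is passed between 50% and 45%.

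**4. The matched-control comparison.** For 25% against 50% with 29 per group, treated as independent groups and two-sided 0.05, power is 39% (Fisher exact) or 49% (chi-square). Exact McNemar with zero within-pair correlation also gives 39%.

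The two analyses can differ on the same data. At 8 of 29 the rule passes. Against 15 of 29 controls (52%, close to the planning rate), Fisher p = 0.11, chi-square p = 0.06, and the unmatched difference is −24.1 points (Newcombe 95% CI −45.4 to 0.9).

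**5. Entry alignment.** Suppose a fraction d of floor admissions go to ICU before a comparable infusion time, the rate counted from admission is 50%, and plasma has no effect. Those patients leave the plasma group but count as events among controls. The recipient rate is then (0.50 − d)/(1 − d):

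| Assumed d | Recipient rate | Built-in gap |
|---|---|---|
| 5% | 47.4% | 2.6 points |
| 10% | 44.4% | 5.6 points |
| 20% | 37.5% | 12.5 points |

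This isolates one difference. It treats every early deteriorator as an ICU transfer, although needing more than 6 L/min is not defined in the documents as an ICU transfer.

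**The case against.** A fixed-null single-arm rule is a legitimate phase II design, and section 2.3 speaks only of preliminary efficacy. The 29 and the 80% follow from a standard formula, and if 50% is right the printed rule is conservative. All of that stands. It limits the power fault to a misstatement; it does not make the 80% true of the printed rule.

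A reader might infer that 29 patients cannot give 80% power within a two-sided 0.05 under any exact rule. That is too strong. Rejecting at 9 or fewer, or at 21 or more, has total error 0.031 + 0.012 = 0.043 at 50% and power 83.4% at 25%. The shortfall belongs to the printed cut-off, or to any cut-off with each tail held to 0.025.

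A reader might also infer that the plan leaves wholly open which analysis decides on ICU transfer. The documents lean further than that: the fixed null is the only printed ICU decision rule, and categorical clinical endpoints receive only frequencies and percentages. The natural reading is that the rule decides and the controls are descriptive. What is missing is the explicit statement, and an interval for the comparison.

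Finally, a reader might conclude that the control group is biased towards plasma. The removal rule alone does push that way, but controls need not have respiratory symptoms, so they may be milder, which pushes against plasma. No document figure sizes either effect.

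**Conclusion.** The point holds in this form. The printed rule has exact power 71.3%, which is 8.7 points below the stated 80%. That follows from the plan's own numbers and needs no assumption.

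The 50% is unsourced, and the rule's false-positive rate moves from 0.3% to 26.5% as the untreated rate goes from 55% to 35%. The dependence is certain; which rate applies is unknown.

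The 80% does not extend to the matched-control comparison, where unmatched power is about 39–49% if 25% against 50% is true. Entry is misaligned between recipients and controls. The removal rule alone builds in 2.6 to 12.5 points for assumed d of 5–20%, but the net direction of bias across all entry differences cannot be determined from the documents.

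None of this shows that the single-arm design is invalid, or that the true untreated rate is below 50%.

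**What to change.** In sections 7.1 and 9.1:

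- Restate the power of the 8-of-29 rule as 71% exact, with one-sided error 1.2% at 50%, and say that it applies only to the fixed-null rule.
- Give the source of the 50% or label it an assumption. Tabulate the rule's false-positive rate for untreated rates on both sides of 50%, as in step 3.
- State that the fixed-null rule governs the ICU-transfer conclusion. Report the control comparison descriptively, as a difference with a 95% confidence interval that allows for the matching and for sampling error in the controls. Do not claim superiority over controls from the rule alone.

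In section 4.3, apply the recipients' entry conditions (respiratory symptoms, not in ICU, not ventilated, 6 L/min or less) to controls at a time after admission comparable to infusion, and disclose the confounding that remains.

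The cost is a less favourable stated power, one short table, and a little more analysis and chart review. No extra recipients are required. If the sponsor prefers to restore 80%, 30 patients with a cut-off of 9 gives 80.3% at 0.025 per tail. That figure is a peak caused by discreteness: exact power falls to 77.1% at 31 and 73.7% at 32, so it should not be adopted without that caveat.

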2. Age \geq 18 years of age
3. No receipt of convalescent plasma

Immunologic Controls:

1. PBMCs with 5-10 million cryopreserved cells per specimen present in the prospective COVID 19 Biorepository
2. Serum or plasma 500 UI each from up to 50 patients present in the COVID-19 Biorepository

Assessment and Data Acquisition:

1. Baseline: Age, sex, comorbidities, date of symptom onset, known COVID-19 contact, type of admission to the floor or ICU, APACHE score (ICU scoring system to classify disease severity and mortality risk), SOFA score (mortality prediction score based on organ function), clinical status, vital signs including temperature, respiratory rate, oxygen saturation, oxygen requirement, neutrophil count, lymphocyte count, CRP, chest x-ray, chest CT, location in hospital.
2. Safety and efficacy: Day 0 (baseline), 1, 2, 3, 4, 7, 14, 21, and 28 and once at day 60.
3. SARS-CoV-2 PCR from OP or NP swabs: Day 0, 4, 7, 14 and at any time when there is clinical suspicion for COVID-19.
4. Outcome measures: increased O₂ requirement (PaO₂/FiO₂ ratio or SpO₂/FIo₂), supplemental oxygen strategy (nasal cannula, high flow nasal cannula, noninvasive ventilation, intubation and invasive mechanical ventilation, rescue ventilation i.e. neuromuscular blocking agents, prone positioning, corticosteroids, ECMO), vasopressors, renal support, ICU LOS, ICU mortality, hospital LOS, hospital mortality, 28 day mortality.
5. Serum or plasma antibody titer² to SARS-CoV-2: Day 0, 7, 14, and 28. Samples from the COVID-19 Biorepository from non-transfused patients will be assayed at two similar timepoints as Immunologic Controls.
6. Blood for immune evaluations of cellular and humoral immunity before CIP infusion (day 0) and 7, 14 and 28 days after CIP infusion. Immune testing may be done at any time if the PI determines there is a need to evaluate acute immune responses (cytokines/chemokines levels). Samples from the Prospective COVID-19 Biorepository from non-transfused patients will be assayed at two similar timepoints as Immunologic Controls.
7. "Clinical controls" will have all relevant datapoints collected via chart review (i.e. biospecimens will not be collected prospectively)

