4.0 ELIGIBILITY

4.1 Inclusion Criteria for Enrollment as a Plasma Recipient

- Patients must be 18 years of age or older
- Patients hospitalized with COVID-19 respiratory symptoms and confirmation via SARS-CoV-2 RT-PCR testing.

- Patient positive for COVID-19 with respiratory symptoms within 72 hours of admission (not in ICU or on high flow oxygen)
- Patient or surrogate is willing and able to provide written informed consent and comply with all protocol requirements.
- Patients with hematologic malignancies or solid tumors are eligible.
- Patients with autoimmune disorders are eligible.
- Patients with immunodeficiency or organ or stem cell transplant are eligible.
- Patients who have received or are receiving hydroxychloroquine or chloroquine are eligible (will be taken off the drug at enrollment)
- Prior use of IVIG is allowed but the investigator should consider the potential for a hyper-coagulable state

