4.2 Exclusion Criteria for Plasma Recipients

- Patients requiring mechanical ventilation or >6 liters per minute nasal cannula oxygen
- Patients on other anti-COVID-19 treatment trials (for example, those being treated with tocilizumab (anti-IL-6 receptor), Siltuximab (anti-IL-2), or Remdesivir).
- A pre-existing condition or use of a medication that, in the opinion of the site investigator, may place the individual at a substantially increased risk due to study participation
- Contraindication to transfusion or history of prior reactions to transfusion blood products.
- Medical conditions for which receipt of 500-600 mL of intravenous fluid may be dangerous to the subject (e.g., decompensated congestive heart failure).

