7.3 Endpoints

7.3.1 Primary Endpoints

- Transfer to ICU
- 28 day mortality

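### The 50% null for ICU admission has no stated source and is not limited to the floor patients the trial enrolls, so the rule of 8 or fewer in 29 may not hold its stated error

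*Combined protocol and SAP*

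**What the plan says.** Section 7.1 of the combined protocol and SAP claims 80% power with 29 evaluable patients for a "significant decrease in ICU admissions from a historical control of 50% of hospitalized patients to 25% with a two-sided type I error of 0.05". Section 9.1 repeats the calculation and the decision rule: "reject ICU admission rate=50% if only 8 or less patients are admitted to ICU among 29 evaluable patients". This is the only efficacy decision rule in the plan.

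The patients it is applied to are defined more narrowly:

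- The Summary (section 1.0) requires a non-ICU floor bed, and section 4.1 requires recipients to be "within 72 hours of admission (not in ICU or on high flow oxygen").
- Section 4.2 excludes "Patients requiring mechanical ventilation or >6 liters per minute nasal cannula oxygen".
- Section 5.2.6 removes patients who pass the oxygen limit or need ventilation before plasma is given.

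The primary endpoint in section 7.3.1 is "Transfer to ICU", alongside 28-day mortality. The baseline data in the Summary include "type of admission to the floor or ICU", so direct ICU admission is a category the plan recognises.

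Section 4.3 describes chart-review controls who were in floor beds and within the same oxygen and ventilation limits on admission. Section 7.1 says that 29 of them will be matched on gender and age. Section 9.1 specifies no test of ICU transfer against them.

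**The concern.** In a single-arm trial with a fixed null, the whole inference rests on that null being the rate eligible patients would have without treatment. The plan describes the 50% only as a rate in hospitalized patients. Nothing ties it to floor patients or to an oxygen level.

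A patient admitted straight to ICU would count in an ICU-admission rate for hospitalized patients but could not enter this trial. The same holds for a patient above 6 L/min. If such patients are in the 50%, the untreated rate among eligible patients is below 50%. Part or all of an observed fall could then come from the eligibility limits and the removal rule, and the decision rule would credit it to plasma. The 25% target could also lie closer to the untreated rate than the plan assumes.

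**Working it through.** **Inputs from sections 7.1 and 9.1.** Null p0 = 0.50, alternative p1 = 0.25, two-sided alpha 0.05, n = 29, success if X ≤ 8.

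**Step 1: reproduce the plan's figure.** One-sample normal approximation:

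n = [(1.960 × √(0.5 × 0.5) + 0.842 × √(0.25 × 0.75)) / (0.50 − 0.25)]² = 28.92, so 29. Power at n = 29 is 80.1%. The stated sample size reproduces.

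**Step 2: exact properties of the printed rule at the stated null.** With X binomial(29, p):

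- P(X ≤ 8 | 0.50) = 0.0121, within the lower-tail limit of 0.025.
- P(X ≤ 8 | 0.25) = 0.713, so exact power is 71%, not 80%.
- A cut-off of 9 would give 83.4% power, but a lower-tail error of 0.0307.

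**Step 3: error of the rule if the untreated rate in eligible patients is not 50%.** The documents give no such rate, so it is an assumption, shown over a range. With no plasma effect:

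| Assumed untreated rate | P(X ≤ 8 of 29) |
|---|---|
| 50% | 1.2% |
| 45% | 4.3% |
| 40% | 11.9% |
| 35% | 26.5% |
| 30% | 47.9% |

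The error passes 2.5% at a true rate of about 47%.

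**Step 4: how a lower rate could arise.** Assume that 50% of hospitalized patients reach ICU and that a share d of them all go there directly. The floor-to-ICU rate is then (0.50 − d)/(1 − d).

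- d = 5%: 0.45/0.95 = 47.4%, error 2.4%
- d = 10%: 0.40/0.90 = 44.4%, error 4.8%
- d = 20%: 0.30/0.80 = 37.5%, error 18.2%
- d = 30%: 0.20/0.70 = 28.6%, error 54.7%

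The documents do not give d. This step does not count the oxygen limit or the removal before infusion.

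**Step 5: the rule under a lower null at n = 29.** The cut-off is the largest c with P(X ≤ c | null) ≤ 0.025, and power is for a halving of the null.

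| Null | Cut-off | Exact error | Power |
|---|---|---|---|
| 45% | 7 or fewer | 1.7% | 68% |
| 40% | 6 or fewer | 2.3% | 64% |
| 33.3% | 4 or fewer | 1.6% | 46% |

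The comparator for these powers is the present rule's exact 71%, not the stated 80%.

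**The case against.** A reader might infer that the 50% is the rate among all hospitalized patients, ICU admissions included, and that the null is therefore shown to belong to a different population. The documents do not say that. Sections 7.1 and 9.1 do not use the word all. Section 2.3 uses historical control group for the chart-review comparator, and in section 7.1 the sentence after the rule describes that matched group, which section 4.3 confines to floor patients within the oxygen limit. The protocol also calls its own enrollees hospitalized patients. The 50% could be a floor-patient rate. If so, one sentence giving its source would settle the matter, but the plan does not contain it.

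Nor do the documents support the inference that ICU admission and ICU transfer are different events. Sections 5.1 and 11.1 use ICU admissions for enrolled patients, and the decision rule itself counts patients admitted to ICU.

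The direction is not certain either. Recipients must have respiratory symptoms, immunocompromised patients are eligible, and section 11.1 describes patients at high risk of needing ICU. These features could raise the untreated rate. At a true 50% the rule is conservative.

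The control group is a partial safeguard, because it would show a low untreated rate. It does not protect the decision, since no stated test or rule uses it for ICU transfer. Controls are also screened only on admission, whereas recipients must stay within the limits until infusion.

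Finally, a chart-review rate is itself uncertain. If 12 of 29 controls were transferred (41%), the exact 95% interval would be about 24% to 61%. That stands, and it shapes the fix.

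**Conclusion.** The point holds as a gap with a likely, but unproven, mismatch. The only efficacy rule rests on a 50% with no stated source or population, while eligibility and removal before infusion select patients at lower acuity. Ordinary reading of the wording makes a lower untreated rate plausible. The stronger reading, that the error is already inflated, is not established, because it depends on a rate the documents do not give.

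The rule tolerates only a small departure: its 1.2% error at 50% passes 2.5% at about 47% and reaches 11.9% at 40%. These figures assume independent patients, 29 evaluable and no plasma effect. This should be fixed, because applying the rule as written could credit plasma with an effect of the eligibility limits.

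**What to change.** 1. In sections 7.1 and 9.1, state the source of the 50% and the population it describes.
2. Unless it is already a rate for floor patients within the limits of sections 4.1 to 4.3, replace it with the ICU-transfer rate among all eligible chart-review controls, not only the 29 matched ones. Count transfers from a start time comparable to infusion, and fix the rate before recipient outcomes are summarised.
3. Report that rate with its confidence interval and show the result of the test at the interval's limits, so that the rate is not treated as known. Report the recipient-versus-control difference with its interval beside the rule.
4. Restate the exact cut-off and power at n = 29 for the chosen null, as in Step 5, and note that the present rule has 71% exact power at 25%.
5. If 50% is kept, say that meeting the rule shows only a rate below 50% and is not by itself evidence of a plasma effect. Report the rule's error at 35% to 45% (26.5% to 4.3%) beside it.

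The cost is protocol and SAP wording plus a tabulation of charts already due for review. No extra patients are needed. The price is a stricter cut-off and lower stated power. Keeping 80% exact power for a halving would instead need 45 patients at a null of 40%, or 61 at 30%.
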